#### **9.2.5 SAEs (Including Deaths) and Adverse Events Leading to Study Drug Discontinuation**

All serious adverse events (SAEs), deaths, and adverse events leading to discontinuation of study drug will be listed. The number and percentage of subjects experiencing SAEs (including deaths) and adverse events leading to discontinuation of study drug will be tabulated by SOC and PT or each treatment group.

#### **9.2.6 Adverse Events of Special Interest**

The Adverse Events of Special Interest (AESI) categories will be summarized and presented by "as treated" treatment group and overall using SOC and MedDRA PT. The AESI categories will be identified by the following search criteria per Standard MedDRA Queries (SMQs)/Company MedDRA Queries (CMQs) in [Appendix B](#).

#### **9.2.7 Adverse Events by Maximum Severity**

TEAEs will also be summarized by maximum severity by "as treated" treatment group and overall. If a subject has an AE with an unknown severity, then the subject will be counted in the severity category of unknown, even if the subject has another occurrence of

the same event with a severity present. The only exception is that if the subject has another occurrence of the same AE with the most extreme severity – severe. In this case, the subject will be counted under the severe category.

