An important medical event that may not be immediately life-threatening or result in death or hospitalization, but based on medical judgment may jeopardize the subject and may require medical or surgical intervention to prevent any of the outcomes listed above (i.e., death of subject, life threatening, hospitalization, prolongation of hospitalization, congenital anomaly, or persistent or significant disability/incapacity). Additionally, any elective or spontaneous abortion or stillbirth is considered an important medical event. Examples of such events include allergic bronchospasm requiring intensive treatment in an emergency room or at home, blood dyscrasias or convulsions that do not result in inpatient hospitalization, or the development of drug dependency or drug abuse.

All AEs reported from the time of study drug administration until 30 days after discontinuation of study drug administration will be collected, whether solicited or spontaneously reported by the subject. In addition, SAEs and protocol-related nonserious AEs will be collected from the time the subject signs the study-specific informed consent.

AbbVie will be responsible for Suspected Unexpected Serious Adverse Reactions (SUSAR) reporting for the Investigational Medicinal Product (IMP) in accordance with global and local requirements.

AEs will be monitored throughout the study to identify any of special interest that may indicate a trend or risk to subjects.

Adverse Events of Special Interest

The following adverse events of special interest (AESI) will be monitored during the study:

- Serious infections
- Opportunistic infections
- Herpes zoster
- Tuberculosis
- Malignancy (all types)
- Gastrointestinal perforations
- Adjudicated cardiovascular events (e.g., major adverse cardiovascular event [MACE])
- Anemia
- Neutropenia

- Lymphopenia
- Increased serum creatinine and renal dysfunction
- Hepatic events and increased hepatic transaminases
- Elevated creatine phosphokinase
- Embolic and thrombotic events (non-cardiac, non-CNS)

Adverse Event Severity and Relationship to Study Drug

The investigator will rate the severity of each AE according to the Rheumatology Common Toxicity Criteria v.2.0. **If no grading criteria are provided for the reported event, then the event should be graded as follows:**

- Mild (Grade 1): Asymptomatic or mild symptoms; clinical or diagnostic observations only; intervention not indicated.

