- Moderate (Grade 2): Minimal, local or noninvasive intervention indicated; limiting age-appropriate instrumental activities of daily living (ADL) (instrumental ADL refer to preparing meals, shopping for groceries or clothes, using the telephone, managing money, etc.).
- Severe (Grade 3): Severe or medically significant but not immediately life-threatening; hospitalization or prolongation of hospitalization indicated; disabling; limiting self care ADL (self care ADL refer to bathing, dressing and undressing, feeding self, using the toilet, taking medications, and not bedridden);
- Life-threatening (Grade 4): Urgent intervention indicated or death related to AE.

The investigator will use the following definitions to assess the relationship of the AE to the use of study drug:

Reasonable Possibility – After consideration of factors including timing of the event, biologic plausibility, clinical judgment, and potential alternative causes, there is sufficient evidence (information) to suggest a causal relationship.

No Reasonable Possibility – After consideration of factors including timing of the event, biologic plausibility, clinical judgment, and potential alternative causes, there is insufficient evidence (information) to suggest a causal relationship.

Pregnancy

While not an AE, pregnancy in a study subject must be reported to AbbVie within 1 working day after the site becomes aware of the pregnancy. Subjects who become pregnant must be discontinued (Section 5.5). Information regarding the pregnancy and the outcome will be collected.

The pregnancy outcome of an elective or spontaneous abortion, stillbirth, or congenital anomaly is considered a SAE and must be reported to AbbVie within 24 hours after the site becomes aware of the event.

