### **9.2.2 Adverse Event Overview**

The number and percentage of subjects experiencing TEAEs will be summarized by treatment group as specified in Section 6.0 and overall.

An overview of AEs will be presented consisting of the number and percentage of subjects experiencing at least one event for each of the following AE categories:

- All TEAEs
- Treatment-emergent serious adverse events (SAEs)
- Treatment-emergent severe adverse events
- TEAEs reasonably possibly related to study drug
- TEAEs of special interest (AESIs)
- TEAEs leading to discontinuation of study drug

- TEAE leading to death
- All deaths

Additional AEs may be considered for tabulation/summary based on recommendations from Clinical and Safety as deemed appropriate.

For AESIs, the point estimate and 95% CI (using normal approximation) will be provided for the treatment difference in AE percentages.

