**Table C-1. OMERACT Criteria**

Rheumatology Common Toxicity Criteria v.2.0 Based on Woodworth TG, et al. Standardizing assessment of adverse effects in rheumatology clinical trials II. Status of OMERACT Drug Safety Working Group May 2006: OMERACT 8. Standardizing Assessment and Reporting of Adverse Effects in Rheumatology Clinical Trials: Enabling Description of Comparative Safety Profiles for Antirheumatic Therapies				
	1 – Mild	2 – Moderate	3 – Severe	4 – Includes Life Threatening
	Asymptomatic, or transient Short duration (< 1 week) No change in life style No medication or OTC	Symptomatic Duration (1 – 2 weeks) Alter lifestyle occasionally Meds relieve. (may be prescription), Study drug continued	Prolonged symptoms, reversible, major functional impairment Prescription meds/partial relief May be hospitalized < 24 hr Temporary study drug discontinuation, or/and dose reduced	At risk of death Substantial disability, especially if permanent. Multiple meds Hospitalised > 24 hr Study drug discontinued
A. Allergic/Immunologic				
A1. Allergic reaction/hypersensitivity (includes drug fever)	Transient rash: drug fever < 38°C: transient, asymptomatic bronchospasm	Generalised urticaria responsive to meds; or drug fever > 38°C, or reversible bronchospasm	Symptomatic bronchospasm requiring meds; symptomatic urticaria persisting with meds, allergy related oedema/angioedema	Anaphylaxis, laryngeal/pharyngeal oedema, requiring resuscitation
A2. Autoimmune reaction	Serilogic or other evidence of autoimmune reaction, but patient asymptomatic: all organ function normal and no treatment is required (e.g., vitiligo)	Evidence of autoimmune reaction involving a non-essential organ or functions, requiring treatment other than immunosuppressive drugs (e.g., hypothyroidism)	Reversible autoimmune reaction involving function of a major organ or toxicity requiring short term immunosuppressive treatment (e.g., transient colitis or anaemia)	Causes major organ dysfunction, or progressive, not reversible, or requires long-term administration of high dose immunosuppressive therapy

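### SAP 9.2.7 names 'severe' as the most extreme AE severity; read literally, a Grade 3 record overrides 'unknown' but a Grade 4 record does not

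*SAP*

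**What the plan says.** Protocol 6.1 sets the severity scale: "The investigator will rate the severity of each AE according to the Rheumatology Common Toxicity Criteria v.2.0". For events those criteria do not cover, it gives a four-grade fallback. The third level is "Severe (Grade 3): Severe or medically significant but not immediately life-threatening" and the fourth is "Life-threatening (Grade 4): Urgent intervention indicated or death related to AE". SAP Table C-1 reproduces the Rheumatology criteria in the same order: after the column for severe comes a last column headed "4 – Includes Life Threatening".

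SAP 9.2.7 covers the table of TEAEs by maximum severity. If a subject has an AE of unknown severity, "then the subject will be counted in the severity category of unknown", even when another record of the same event does carry a severity. "The only exception is that if the subject has another occurrence of the same AE with the most extreme severity", and the SAP names that severity as severe. "In this case, the subject will be counted under the severe category".

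Two other parts of the SAP bear on this. Sections 9.2 and 9.2.3 say that when the same event recurs in a subject, the highest severity is the one reported. Sections 9.2.2 and 9.2.3 also plan a row or table called "Treatment-emergent severe adverse events", with no grade attached.

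**The concern.** The exception in 9.2.7 is meant to stop a missing severity from hiding a subject's worst recorded event. It does so by naming the top category, but it names the third of four. Applied as written, it protects a Grade 3 record and not a Grade 4 record. A table intended to show each subject's worst severity could then show a subject with a life-threatening event as unknown.

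Long-term safety is part of the primary objective, so the severity table should be right at its top end. The text is also open to more than one programming, because the SAP never maps the four grades to the categories of its AE tables.

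**Working it through.** No sample size, alpha or event count enters the main point. The check is to apply the rule to each possible pair of records.

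**Inputs**
- Scale: Grades 1 to 4, with severe = Grade 3 and life-threatening = Grade 4 (Protocol 6.1; same order in SAP Table C-1).
- Default: unknown outranks any other recorded severity of the same AE (SAP 9.2.7).
- Exception: a record at the most extreme severity, named as severe, outranks unknown, and the subject is counted as severe (SAP 9.2.7).
- General rule: for a recurring AE, report the highest severity (SAP 9.2 and 9.2.3).

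**Case: one subject, one AE, one record of unknown severity plus one graded record**

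| Graded record | 9.2.7, severe = Grade 3 (protocol label) | 9.2.7, severe = Grade 3 or 4 | 9.2.7, most extreme = Grade 4 only | Highest recorded grade (9.2, 9.2.3) |
|---|---|---|---|---|
| Grade 1 | unknown | unknown | unknown | Grade 1 |
| Grade 2 | unknown | unknown | unknown | Grade 2 |
| Grade 3 | severe | severe | unknown | Grade 3 |
| Grade 4 | **unknown** | severe | severe | Grade 4 |

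1. Under the protocol's own label (first reading), the rule is not monotone: Grade 3 overrides unknown and Grade 4 does not.
2. Under the second reading that fault disappears, but the SAP nowhere says that severe includes Grade 4, and the table would merge the top two grades under one label.
3. Under the third reading, a Grade 4 subject is counted under a label that the protocol gives to Grade 3.
4. None of the three readings of 9.2.7 matches the general rule in the last column. The SAP does not say which prevails; 9.2.7 is the more specific text, so a programmer would normally follow it.

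**What other outputs show.** SAP 9.2.2 counts treatment-emergent SAEs, TEAEs leading to death and all deaths. Sections 9.2.3 and 9.2.5 tabulate SAEs, and 9.2.5 and 9.2.11 list SAEs and deaths. Death and life-threatening events are SAE criteria in Protocol 6.1, so they appear there whatever 9.2.7 does. Grade 4 is not the same set as serious, however. In Table C-1 an ALT or AST above 8 × ULN, neutrophils or lymphocytes below 0.5 (× 1000), or a haemoglobin fall of at least 3.0 g/dl is Grade 4 on the value alone. None of these values is in itself an SAE criterion, although an investigator may judge such an event medically important and therefore serious. A non-serious Grade 4 AE of this kind could be misplaced in the severity table without appearing among the SAEs; the value itself would still be graded in the laboratory tables under SAP 9.3.

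**Weight of one subject.** Protocol 7.3 and SAP 2.4 equate 40 subjects with 20% and 120 with 60%: 40 / 0.20 = 200 and 120 / 0.60 = 200. Six treatment sequences, assumed equal in size, give 200 / 6 ≈ 33 per group, and 1 / 33 ≈ 3.0 percentage points. That is what one subject counts for in a group of that assumed size. It says nothing about how many subjects would be affected.

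**The case against.** The strongest reply is that the intent is plain. The principle in 9.2.7 is that the top category overrides unknown, and the wording fits a mild, moderate, severe display in which severe absorbs Grade 4. SAP 9.2.8 has the same structure for relationship to study drug, where the exception does name the top category. The highest-severity text in 9.2 and 9.2.3 points the same way. On that view a Grade 4 record falls to unknown only if severe is held to mean exactly Grade 3 and the words about the most extreme severity are set aside.

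This is probably what the authors meant, and it limits the importance of the point. It does not remove it. The SAP never states a three-level display or a mapping from four grades to three. The protocol and the SAP's own Table C-1 use severe for the level below the top, and the general rule does not displace the specific one.

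Three stronger readings are tempting and are not supported:
- A reader might infer that the severe rows in 9.2.2 and 9.2.3 cover Grade 3 only and so leave out Grade 4. Those rows name no grade; the term is undefined, which is a lesser fault. The unknown rule is also written for the 9.2.7 table alone, and the 9.2.2 overview counts subjects with at least one event in a category, so the rule does not move that row.
- A reader might infer that the worst events drop out of the safety report. SAEs, fatal TEAEs and deaths are counted and listed separately.
- A reader might take 3.0 percentage points as the expected distortion. It is the weight of one subject under an assumption of equal groups.

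**Conclusion.** The point stands as a minor drafting error. SAP 9.2.7 identifies the wrong category as the most extreme and, taken literally, gives a wrong result for one combination of records: unknown plus Grade 4 of the same AE in the same subject. It also conflicts with the highest-severity rule elsewhere in the SAP.

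The effect is probably rare, though the documents give no rate of missing severity or of Grade 4 events from which to estimate it. It is confined to the maximum-severity table. The subjects whose placement could be wrong without also showing among the SAEs are those with non-serious Grade 4 AEs, most plausibly laboratory-based ones. The conclusion rests on reading severe as the protocol and Table C-1 label it. If the SAP stated that severe includes Grade 4, the misclassification would not arise.

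**What to change.** In SAP 9.2.7, replace the exception with a statement that any Grade 3 or Grade 4 record of the same AE overrides unknown, and that the subject is counted at the highest recorded grade. Add that, for unknown severities, this rule takes precedence over the general highest-severity text in 9.2 and 9.2.3, so that the sections agree.

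As a clarification, state in 9.2.2 and 9.2.3 that severe means Grade 3 or higher. The TEAE overview is among the key safety outputs of the interim analysis in SAP 11.0, so the definition should be settled before that is programmed.

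Showing Grade 4 as its own category in the severity table is an optional display choice and is not needed to correct the rule.

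The cost is a few sentences of SAP text and the matching line in the programming specification. No new data, protocol amendment or change to study conduct is required.

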### **9.2.8 Adverse Events by Maximum Relationship**

TEAEs will also be summarized by maximum relationship to treatment, as assessed by the investigator, by "as treated" treatment group and overall. If a subject has a TEAE with an unknown relationship, then the subject will be counted in the relationship category of "unknown," even if the subject has another occurrence of the same event with a relationship present. The only exception is if the subject has another occurrence of the same TEAE with a relationship assessment of "reasonable possibility." In this case, the subject will be counted under the "reasonable possibility" category.

### **9.2.9 Adverse Events by "Reasonably Possibly Related" Relationship**

TEAEs and reasonably possibly related AEs occurring for more than 2% of the subjects in any of the treatment groups will also be summarized by MedDRA SOC and PT. If a subject has an AE with an unknown relationship, then the subject will be counted in as 'related.'

### **9.2.10 Frequent (> 5%) Adverse Events and Reasonably Possibly Related Adverse Events by Preferred Term in Decreasing Frequency**

TEAEs and reasonably possibly related AEs occurring for more than 5% of the subjects in any of the treatment arms will be summarized by MedDRA PT in decreasing frequency separately.

### **9.2.11 Listing of Adverse Events**

The following additional summaries of AEs will be prepared.

- Listing of Subjects with Treatment-Emergent AESIs

- Listing of Subjects with Pretreatment SAEs
- Listing of Subjects with Treatment-Emergent SAEs
- Listing of Treatment-Emergent AEs that led to discontinuation of study drug
- Listing of all deaths.

### **9.3 Analysis of Laboratory Data**

Data collected from central and local laboratories, including additional laboratory testing due to an SAE, will be used in all analyses, except for Baseline, where SAE-related laboratory assessments on or before the first dose of study drug will be excluded.

Baseline is defined as the last available measurement before Study M16-063 study drug administration. The clinical laboratory tests defined in the protocol operations manual (e.g., hematology and clinical chemistry) will be summarized.

Mean change from baseline to each applicable post-baseline visit will be summarized for selected laboratory variables, with the number of observations, baseline mean, and visit mean, at each visit in Study M16-063 and Study M16-763 for each treatment group. An ANOVA model with only treatment as a factor, not controlling for baseline, will be used to test statistical significance for the mean change from baseline among different arms.

The baseline and post-baseline laboratory observations will be categorized as Grade 1, Grade 2, Grade 3, and Grade 4 according to OMERACT criteria (Rheumatology Common Toxicity Criteria v.2.0). For creatine phosphokinase and creatinine, NCI CTC criteria will be used.

For each laboratory variable, shift tables will be generated that cross tabulate the subjects as deemed appropriate by "as treated" treatment group:

- Category of the baseline value versus category of the final value.
- Category of the baseline value versus maximum category.
- Category of the baseline value versus minimum category.

Note that the minimum/maximum category is used, rather than the category of the minimum/maximum value. The two may be different due to variation in the reference range.

No statistical tests will be performed for this analysis.

Laboratory abnormalities will be evaluated based on Potentially Clinically Significant (PCS) criteria ([Appendix C](#)). For each laboratory PCS criterion, the number and percentage of subjects who have a laboratory value meeting the criteria will be summarized. Listings will be provided to summarize subject-level laboratory data for subjects meeting PCS criteria.

According to FDA's Guidance for Industry "Drug-Induced Liver Injury: Premarketing clinical evaluation" (July 2009), when aminotransferase (AT) abnormalities indicating hepatocellular injury are accompanied by evidence of impaired hepatic function (bilirubin elevation  $> 2 \times \text{ULN}$ ), in the absence of evidence of biliary obstruction (i.e., significant elevation of ALP) or some other explanation of the injury (e.g., viral hepatitis, alcohol hepatitis), the combined finding (i.e., Hy's Law cases) represents a signal of a potential for the drug to cause severe DILI.

For the purpose of assessing for potential Hy's law cases, the frequencies and percentages of subjects with post baseline liver-specific function test values that meet the following criteria of potential clinical interest will be summarized by "as treated" treatment group:

- $\text{ALT} \geq 3 \times \text{ULN}$
- $\text{ALT} \geq 5 \times \text{ULN}$
- $\text{ALT} \geq 10 \times \text{ULN}$
- $\text{ALT} \geq 20 \times \text{ULN}$
- $\text{AST} \geq 3 \times \text{ULN}$
- $\text{AST} \geq 5 \times \text{ULN}$
- $\text{AST} \geq 10 \times \text{ULN}$
- $\text{AST} \geq 20 \times \text{ULN}$

- Total Bilirubin Level (TBL)  $\geq 2 \times$  ULN
- Alkaline phosphatase  $\geq 1.5 \times$  ULN
- ALT and/or AST  $\geq 3 \times$  ULN and concurrent TBL  $\geq 1.5 \times$  ULN
- ALT and/or AST  $\geq 3 \times$  ULN and concurrent TBL  $\geq 2 \times$  ULN

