5.6 Follow-Up for Subject Withdrawal from Study

To minimize missing data for efficacy and safety assessments, subjects who prematurely discontinue study drug treatment should continue to be followed for all regularly scheduled visits, unless subjects have decided to discontinue the study participation entirely (withdrawal of informed consent). Subjects should be advised on the continued scientific importance of their data even if they discontinue treatment with study drug early.

Following discontinuation of study drug, the subject should be treated in accordance with the investigator's best clinical judgment irrespective of whether the subject decides to continue participation in the study. In addition, all future rescue- and efficacy-driven discontinuation criteria no longer apply. This includes 20% TJC/SJC calculations at Weeks 12 through 24, Weeks 36 through 40 and Week 48 and thereafter, as well as CDAI calculation at Week 26, if applicable. If at any point a subject no longer wants to provide assessments (withdrawal of informed consent) following discontinuation of study drug, a second PD visit is not required.

If a subject prematurely discontinues study participation (withdrawal of informed consent), the procedures outlined for the PD visit should be completed as soon as possible, preferably within 2 weeks. In addition, if subject is willing, a 30-day follow-up phone call after the last dose of study drug may be completed to ensure all treatment-emergent AEs/SAEs have been resolved.

All attempts must be made to determine the date of the last study drug dose and the primary reason for discontinuation of study drug or study participation. The information will be recorded on the appropriate electronic case report form (eCRF) page. However, these procedures should not interfere with the initiation of any new treatments or therapeutic modalities that the Investigator feels are necessary to treat the subject's condition. Following discontinuation of study drug, the subject should be treated in accordance with the Investigator's best clinical judgment irrespective of whether the subject decides to continue participation in the study.

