6.2 Toxicity Management

The management of specific AEs and laboratory parameters is described in the Operations Manual.

The toxicity management of AEs, including AESIs, consists of safety monitoring (review of AEs on an ongoing basis and periodic/ad hoc review of safety issues by a data monitoring committee [DMC]), interruption of study drug dosing with appropriate clinical management (if applicable), and discontinuation of the subjects from study drug. The management of specific AEs and laboratory parameters is described below.

For subjects who have had study drug discontinued and are instead on standard of care therapies, these toxicity management requirements do not apply (including alerts from the central lab), and any intolerability to standard of care therapies should be managed by the prescribing physician.

Serious Infections: Subjects should be closely monitored for the development of signs and symptoms of infection during and after treatment with study drug. Study drug should be interrupted if a subject develops a serious infection or an opportunistic infection. A subject who develops a new infection during treatment with study drug should undergo prompt diagnostic testing appropriate for an immunocompromised subject. As appropriate, antimicrobial therapy should be initiated, and the subject should be closely monitored. Study drug may be restarted once the infection has been successfully treated. Subjects who develop active TB or experience hepatitis B reactivation must be discontinued from study drug. To further monitor subjects for serious infections, subjects will complete at-home weekly temperature monitoring. If above 100.5 degrees Fahrenheit (38 degrees Celsius), subject should inform their study doctor to assess the need for further evaluation.

Subjects should be advised to follow local public health guidelines in order to prevent subjects enrolled in these trials from acquiring TB.

Serious Gastrointestinal Events: Subjects presenting with the onset of signs or symptoms of a serious gastrointestinal event should be evaluated promptly for early identification of gastrointestinal perforation. If the diagnosis of gastrointestinal perforation is confirmed, the subject must be discontinued from study drug.

Cardiovascular Events (MACE): Subjects presenting with potential cardiovascular events should be carefully monitored. These events will be reviewed and adjudicated by the independent CAC in a blinded manner.

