### **9.2.1 Treatment-Emergent Adverse Events**

To summarize data from Study M16-763 only, a treatment-emergent Adverse Event (TEAE) is defined as an adverse event with an onset date that is on or after the first dose of study drug from Study M16-763, and no more than 30 days after the last dose of study drug from Study M16-763.

To summarize a combination of data from Studies M16-063 and M16-763, a treatment-emergent Adverse Event (TEAE) is defined as an adverse event with an onset date that is on or after the first dose of study drug from Study M16-063, and no more than 30 days after the last dose of study drug from Study M16-763.

Events where the onset date is the same as Study M16-063 study drug start date are assumed to be treatment-emergent. If an incomplete onset date was collected for an adverse event, the event will be assumed to be treatment-emergent unless there is other evidence that confirms that the event was not treatment-emergent (e.g., the event end date was prior to the study drug start date).

The number and percentage of subjects experiencing TEAEs will be summarized.

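### The SAP sets no end relative to last dose for laboratory, vital-sign and ECG values, so off-drug values can enter the study-drug arms' safety summaries

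*SAP*

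**What the plan says.** **Laboratory data (SAP 9.3).** The inclusion rule is "Data collected from central and local laboratories, including additional laboratory testing due to an SAE, will be used in all analyses", and the only stated exception concerns Baseline. One shift table uses "Category of the baseline value versus category of the final value"; the others use the maximum and minimum category. For potentially clinically significant (PCS) values, "the number and percentage of subjects who have a laboratory value meeting the criteria will be summarized". The liver table counts "subjects with post baseline liver-specific function test values that meet the following criteria". Mean changes by visit are compared between arms by ANOVA.

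**Vital signs and ECG.** SAP 9.1 asks for means at each protocol visit. SAP 9.4 adds ANOVA tests and PCS counts for vital signs. SAP 9.6 summarises ECG findings by group and visit. None of these sections refers to last dose.

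**Grouping.** SAP 4.0 groups the Safety Analysis Set by treatment received in M16-763 and does not reclassify subjects who stop.

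**Follow-up after stopping.** Under Protocol 5.6, "subjects who prematurely discontinue study drug treatment should continue to be followed for all regularly scheduled visits" unless consent is withdrawn. Protocol Appendix D schedules laboratory tests, vital signs and ECG at each visit from Week 18 to Week 60. Protocol 6.2 adds: "For subjects who have had study drug discontinued and are instead on standard of care therapies, these toxicity management requirements do not apply".

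**Adverse events.** SAP 9.2.1 limits treatment-emergent events to those with onset "no more than 30 days after the last dose of study drug from Study M16-763".

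**The concern.** The laboratory, vital-sign and ECG summaries can cover a longer period than the adverse-event tables beside them, and part of that period is on other therapy. Take a subject who stops at Week 18, starts another treatment and has ALT above 8 x ULN at Week 48. By SAP Table C-1 this is Grade 4. Under the rules as written it enters the old arm's shift table, PCS count and liver rows, while an adverse event with that onset is not treatment-emergent.

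The effect can go either way. Visit means may be diluted as values recover, or shifted by the new therapy. Counts based on any value or the worst category can only rise as more values are added. Both effects depend on how many subjects in an arm stop, so an ANOVA comparison of arms can partly reflect stopping rates. The study's hypothesis is that safety is maintained over extended treatment, and several AESIs (anemia, neutropenia, lymphopenia, CPK, creatinine, transaminases) are measured directly in the laboratory.

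**Working it through.** **1. The plan's own figure.** SAP 2.4 and Protocol 7.3 expect 20-60% of subjects, or 40 to 120, to complete. 40/0.20 = 200 and 120/0.60 = 200, so the base is 200, and 80 to 160 subjects are expected not to complete.

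**2. Which visits fall outside a 30-day window.** For a subject whose last dose is at Week 18, the later visits (24, 30, 36, 48, 60) come 42, 84, 126, 210 and 294 days afterwards. If both ±7-day visit windows are used fully, these become 28, 70, 112, 196 and 280 days. Week 24 can then fall inside the window; Weeks 30 to 60 cannot.

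**3. Off-drug share at Week 60.** Let c be the share completing study drug (0.20-0.60, if that is what the documents mean by completing) and f the share of stoppers who keep attending (not given; assumed 0.25-1.0).

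Share = (1-c)f / [(1-c)f + c]

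| c | f | Off drug | On drug | Off-drug share |
|---|---|---|---|---|
| 0.60 | 0.25 | 20 | 120 | 14% |
| 0.60 | 0.50 | 40 | 120 | 25% |
| 0.60 | 1.0 | 80 | 120 | 40% |
| 0.20 | 0.25 | 40 | 40 | 50% |
| 0.20 | 0.50 | 80 | 40 | 67% |
| 0.20 | 1.0 | 160 | 40 | 80% |

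As f approaches 0, the share approaches 0.

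**4. Share over all six extension visits.** Assume stops are spread evenly over Weeks 18, 24, 30, 36 and 48. The visits left more than 30 days after the stop are 5, 4, 3, 2 and 1, a mean of 3 of 6.
- All stoppers attend: 0.5 x 0.4 = 20% (60% complete) to 0.5 x 0.8 = 40% (20% complete).
- Half attend: 0.4 x 1.5 / (3.6 + 0.4 x 4.5) = 11%, and 0.8 x 1.5 / (1.2 + 0.8 x 4.5) = 25%.

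These shares count extension visits only; the SAP's visit tables also show M16-063 visits.

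**5. Effect on a visit mean (illustration).** Suppose the true on-drug change is 1 unit and values return fully to 0 off drug. The Week 60 mean is then 1 minus the share in step 3: 0.86 to 0.60 if 60% complete, and 0.50 to 0.20 if 20% complete. Two arms with the same on-drug change, but with 60% and 20% completing and all stoppers attending, would read 0.60 and 0.20. That is a difference of 0.40 from stopping alone. The 20-60% is an overall estimate; using its ends for two arms is an assumption.

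**6. Effect on a PCS rate (illustration).** Assume a 3% chance of a PCS value at each visit, on or off drug, with all stoppers stopping at Week 18. Six visits give 1 - 0.97^6 = 16.7%; one visit gives 3%.
- On-treatment rate: 0.2 x 16.7% + 0.8 x 3% = 5.7%, or 0.6 x 16.7% + 0.4 x 3% = 11.2%.
- All-data rate if all stoppers attend: 16.7% in both cases.
- All-data rate if half attend: 11.2% (20% complete) or 14.0% (60% complete).

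**The case against.** **Collecting these data is deliberate.** Protocol 5.6 gives reducing missing efficacy and safety data as the reason for continued visits, and Protocol 3.3 and SAP 3.4 define safety evaluation over the whole study. A whole-study summary therefore has a stated purpose, and the plan does not contradict itself by allowing one. This stands, and is why that summary should be kept.

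**Inclusion is inferred.** The lead sentence of SAP 9.3 concerns the source of laboratory data, not timing. No sentence says that off-drug values count. Inclusion follows from that rule, the absence of any cut-off, the fixed grouping and Protocol 5.6. The inference is sound, but it is an inference.

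**Scope differs by data type.** Shift tables exist for laboratory data only. PCS criteria cover laboratory and vital-sign data, not ECG. ANOVA applies to laboratory and vital-sign means.

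**An on-treatment reading partly exists.** A reader might infer that long-term safety cannot be read from this study at all. The documents do not support that. Treatment-emergent AESIs, SAEs and events leading to discontinuation already use the 30-day limit, and PCS listings let individual late values be traced. Reported events do not, however, replace the laboratory summaries.

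**Different windows are not in themselves an error.** The one-day limit for concomitant medication in SAP 7.3 serves another purpose and adds little here.

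**On-treatment means are selected.** Stopping is largely driven by efficacy criteria (Protocol 5.5), so late on-treatment means describe responders who tolerated the drug. This stands and should be stated with the tables.

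**Conclusion.** The gap is real and should be closed. Followed as written, the SAP lets off-drug values enter the study-drug arm's visit means and ANOVA tests (laboratory, vital signs), shift tables (laboratory), PCS counts (laboratory, vital signs), liver rows and ECG summaries.

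Its size cannot be derived from the documents. The 14-80% range at Week 60 needs two assumptions: that completing the extension means completing study drug, and that 25-100% of stoppers keep attending. The estimate is tied to the discontinuation criteria, which makes the first plausible. If completion instead means study participation, the off-drug share cannot be obtained from that figure. Protocol 5.5 lets non-responders stop drug or leave the study and gives no split between the two. A reader might take 40-80% of Week 60 values, or 20-40% of all extension values, as the expected contamination; both need every stopper to attend. If most leave, the share is near zero.

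The direction is not fixed for means. Any-value and worst-category counts can only rise.

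**What to change.** In SAP 9.1, 9.3 (including the liver table), 9.4 and 9.6, define on-treatment values as those from first dose to last dose + 30 days, matching SAP 9.2.1. For combined M16-063/M16-763 summaries, start at the first M16-063 dose.

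Base the main visit means, ANOVA tests, shift tables (final, maximum and minimum category), PCS counts, liver rows and ECG summaries on that window. Keep the same summaries on all data beside them, labelled as whole-study and supportive, so that the evaluation over the entire study is preserved. State under the late-visit tables that on-treatment means describe subjects selected for response and tolerability, and show the number of subjects on and off drug at each visit.

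The cost is SAP wording, one derived flag and a second set of tables. The flag uses the last-dose date already needed for the exposure formula in SAP 6.0. No new data and no change to subject care are needed. The main tables will have fewer subjects at late visits: at Week 60, with all stoppers attending, 40 to 120 in place of 200.
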